4.4.3 Prohibited Therapy

4.4.3.1 Live or Attenuated Vaccinations

Immunization with a live or attenuated vaccine is prohibited within 6 weeks prior to the first dose of fenebrutinib and during the treatment period.

Seasonal influenza vaccination is permitted if the inactivated vaccine formulation is administered.

4.4.4 Prohibited Food

Use of furanocoumarin derivatives, as found in grapefruit, Seville orange, pomegranate, or star fruit juice or products, is prohibited within 7 days prior to the first dose of fenebrutinib and during the treatment period (i.e., until the final dose of fenebrutinib).

4.5 STUDY ASSESSMENTS

The schedule of activities to be performed during the study is provided in [Appendix 1](#). All activities should be performed and documented for each patient.

All assessments on Day 1 are conducted prior to study drug administration unless otherwise specified. Assessments that were performed at the final visit of the parent study, if within 3 months prior to Day 1, should not be repeated.

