3. STUDY DESIGN

3.1 DESCRIPTION OF THE STUDY

This is a Phase II, multicenter, OLE study to evaluate the long-term safety and efficacy of fenebrutinib in patients with CSU who have completed the treatment period in a fenebrutinib CSU parent study. Patients may enroll in this OLE study at any time after completing the treatment period of the parent study. Up to 165 patients from parent study GS39684 are expected to be enrolled globally.

Patients will receive open-label fenebrutinib at a dose of 200 mg PO BID. Treatment may continue until the end of the study (see Section 3.2).

Because some patients enrolling in this study may be receiving fenebrutinib for the first time (i.e., those patients randomly assigned to placebo in the parent study), all patients will be monitored at Weeks 4, 8, and 12. Thereafter, patients will be monitored approximately every 12 weeks (see Appendix 1).

Patients should maintain a stable dose of standard-of-care H₁-antihistamines (background therapy) for the first 12 weeks of the study. Discontinuation or reduction in the dose of standard-of-care H₁-antihistamines may be attempted at any time after the first 12 weeks, at the investigator's discretion (see Sections 4.3.2.2 and 4.4 for details on background and concomitant therapies).

Monitoring for safety and tolerability will continue throughout the study, including evaluation of clinical laboratory results and assessment of adverse events. Patients with

[figure not shown]
disease worsening, as determined by the investigator, should return to the clinic as soon as possible for an unscheduled visit. The investigator may also conduct an unscheduled visit to assess the patient's disease condition.

Patients who discontinue study treatment (see Sections 4.6.1 and 5.1.2.2) will be asked to return to the clinic for a safety follow-up visit approximately 4 weeks after the last dose of study drug. Patients who refuse to complete the safety follow-up period should return to the clinic for treatment discontinuation visit.

Details regarding assessments at the safety follow-up, treatment discontinuation, and unscheduled visits are provided in Appendix 1.

Figure 1 presents an overview of the study design. A schedule of activities is provided in Appendix 1.

Figure 1 Study Schema

BID = twice a day; BL = baseline; PO = by mouth.

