4.1.1 Inclusion Criteria

Patients must meet the following criteria for study entry:

- Signed Informed Consent Form
- Ability to comply with the study protocol, in the investigator's judgment
- Completion of the treatment period as specified in the parent study
- Acceptable demonstration of tolerance to study drug during the parent study as determined by the investigator or Medical Monitor
- For patients receiving treatment with proton-pump inhibitors (PPIs) or H₂-receptor antagonists (H₂RAs), agreement to maintain treatment at a stable dose for the first 12 weeks of the study
- For women of childbearing potential: agreement to remain abstinent (refrain from heterosexual intercourse) or use contraceptive measures, and agreement to refrain from donating eggs, as defined below:

Women must remain abstinent or use contraceptive methods with a failure rate of < 1% per year during the treatment period and for at least 4 weeks after the final dose of fenebrutinib. Women must refrain from donating eggs during this same period.

A woman is considered to be of childbearing potential if she is postmenarcheal, has not reached a postmenopausal state (≥ 12 continuous months of amenorrhea with no identified cause other than menopause), and has not undergone surgical sterilization (removal of ovaries and/or uterus). The definition of childbearing potential may be adapted for alignment with local guidelines or requirements.

Examples of contraceptive methods with a failure rate of $< 1\%$ per year include bilateral tubal ligation, male sterilization, and copper intrauterine devices.

Hormonal contraceptive methods containing estrogen must be supplemented by a barrier method.

The reliability of sexual abstinence should be evaluated in relation to the duration of the clinical trial and the preferred and usual lifestyle of the patient. Periodic abstinence (e.g., calendar, ovulation, symptothermal, or postovulation methods) and withdrawal are not acceptable methods of contraception.

- For men: agreement to remain abstinent (refrain from heterosexual intercourse) or use a condom, and agreement to refrain from donating sperm, as defined below:

With a female partner of childbearing potential or pregnant female partner, men must remain abstinent or use a condom during the treatment period and for 4 weeks after the final dose of fenebrutinib to avoid exposing the embryo. Men must refrain from donating sperm during this same period.

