4.1.2 Exclusion Criteria

Patients who meet any of the following criteria will be excluded from study entry:

- Pregnant or breastfeeding, or intending to become pregnant during the study or within 4 weeks after the final dose of fenebrutinib
Women of childbearing potential must have a negative urine pregnancy test result prior to initiation of the first dose of study drug.
- Treatment with any investigational agent or live/attenuated vaccine in the preceding 6 weeks
Seasonal influenza vaccination is permitted if the inactivated vaccine formulation is administered.
- Any signs or symptoms of infection judged by the investigator to be clinically significant since completing the treatment period of the parent study
- Any significant changes (e.g., events, changes in medication) occurring after completion of participation in the parent study that, in the investigator's judgment, would increase the risk of adverse events in this OLE study

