4.5.1 Informed Consent Forms and Screening Log

Written informed consent for participation in the study must be obtained before performing any study-related procedures. Informed Consent Forms for enrolled patients and for patients who are not subsequently enrolled will be maintained at the study site.

All screening (Day 1) evaluations must be completed and reviewed to confirm that patients meet all eligibility criteria before enrollment and receiving the first open-label dose in this study. The investigator will maintain a screening log to record details of all patients screened and to confirm eligibility or record reasons for screening failure, as applicable.

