Appendix 1 Schedule of Activities

Week	Study Site Visits ^a Year 1							Study Site Visits ^a Year 2–End of Study				UV	TD ^c	SC/ 4-Week SFU ^d
	1 ^b	4	8	12	24	36	52	12	24	36	52			
Day (Window)	1	28 (±7)	56 (±7)	84 (±7)	168 (±14)	252 (±14)	365 (±14)	84 (±14)	168 (±14)	252 (±14)	365 (±14)			(±14)
Informed consent	x													
Inclusion/exclusion criteria	x													
Concomitant medications ^e	x	x	x	x	x	x	x	x	x	x	x	x	x	x
Adverse events ^f	x	x	x	x	x	x	x	x	x	x	x	x	x	x
Vital signs ^g	x	x			x		x		x		x	(x)	x	x
Weight	x													
Limited physical examination ^h	x	(x)	(x)	(x)	(x)	(x)	(x)	(x)	(x)	(x)	(x)	(x)	(x)	(x)
ECG ⁱ	x						x				x	(x)	x	x
Hematology ^j	x	x	x	x	x	x	x	x	x	x	x	(x)	x	x
Chemistry ^k	x	x	x	x	x	x	x	x	x	x	x	(x)	x	x
Lipid panel	x	x					x				x	(x)	x	x
Coagulation ^l	x						x				x	(x)		
Pregnancy test (urine) women ^m	x	Q4W										(x)	x	x
Urinalysis ⁿ	x	x					x				x	(x)	x	x
UCT ^o	x	x	x	x	x	x	x	x	x	x	x	(x)	x	x
PhyGA-LS ^p	x	x	x	x	x	x	x	x	x	x	x	(x)	x	x
Urticaria Patient Daily Diary ^q	x	x	x	x										
Plasma PK sample ^r	x			x	x		x		x		x	(x)	x	x
Fenebrutinib administration ^s	x	BID												
Fenebrutinib dispensing ^a	x	Q4W												

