Appendix 1: Schedule of Activities (Cont.)

BID=twice a day; CRP=C-reactive protein; CSU=chronic spontaneous urticaria; eCRF=electronic case report form; LDH=lactate dehydrogenase; OLE=open-label extension; PK=pharmacokinetics; PRO=patient-reported outcome; PhyGA-LS=Physician's Global Assessment of Disease Control-Likert Scale; Q4W=every 4 weeks; SC=study completion; SFU=safety follow-up; TD=treatment discontinuation; UAS=Urticaria Activity Score;UAS7=Urticaria Activity Score over 7 days; UCT=Urticaria Control Test; UV=unscheduled visit.

Note: (x)=optional/as clinically indicated.

- ^a Fenebrutinib tablets will be dispensed on site every 4 weeks. For periods in which study site visits (for assessments) are scheduled > 4 weeks apart, patients will be expected to visit site to receive allotment of study drug.
- ^b All assessments on Day 1 are conducted prior to study drug administration unless otherwise specified. Activities that were performed at final visit of the parent study, if within 3 months prior to Day 1, should not be repeated.
- ^c Patients who refuse to complete the safety follow-up period should return to the clinic for a treatment discontinuation visit.
- ^d Patients who discontinue study treatment will be asked to return to the clinic for a safety follow-up visit approximately 4 weeks after the last dose of study drug (see Section 4.6.1).
- ^e Concomitant therapy consists of any medication (e.g., prescription drugs, over-the-counter drugs, vaccines, herbal or homeopathic remedies, nutritional supplements) used by a patient in addition to protocol-mandated treatment from entry into the extension study to the final visit of the extension study. All such medications, including standard-of-care H₁-antihistamines for CSU, should be reported to the investigator and recorded on the Concomitant Medications eCRF.
- ^f After informed consent has been obtained but prior to initiation of study drug, only serious adverse events caused by a protocol-mandated intervention should be reported. After initiation of study drug, all adverse events will be reported until 4 weeks after the final dose of study drug. After this period, the Sponsor should be notified if the investigator becomes aware of any serious adverse event that is believed to be related to prior study drug treatment (see Section 5.6).
- ^g Includes measurement of pulse rate and systolic and diastolic blood pressure while the patient is in a seated position for at least 5 minutes

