Appendix 1: Schedule of Activities (Cont.)

- ^m For women of childbearing potential: urine pregnancy tests will be performed locally at specified visits. The patient will be requested to conduct monthly urine pregnancy tests at the site between in-clinic study visits. If a urine pregnancy test is positive, it must be confirmed by a serum pregnancy test (performed locally).
- ⁿ Includes dipstick (pH, specific gravity, glucose, protein, ketones, blood) and microscopic examination (sediment, RBCs, WBCs, casts, crystals, epithelial cells, bacteria).
- ^o UCT to be self-administered before the patient receives any information on disease status, prior to the performance of non-PRO assessments, and prior to study drug administration, unless otherwise specified.
- ^p The PhyGA-LS reflects the investigator's assessment of the treatment over the previous 4 weeks. It has the following categories: no control, little control, moderate control, good control, and complete control (see [Appendix 4](#)).
- ^q Patient is to complete the Urticaria Patient Daily Diary twice a day, approximately every 12 hours (morning/evening) through Week 12. The UAS is derived from patient entries in the daily diary and is used to calculate the UAS7. The last diary entry may occur the day prior to the Week 12 visit.
- ^r 
- ^s Patients will receive the first dose of fenebrutinib at the Day 1 study visit. Thereafter, fenebrutinib will be self-administered. Fenebrutinib may be taken with or without food. Patients should be instructed that a missed dose should not be taken with the next scheduled dose.

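### The Day 1 no-repeat rule has no exception for the urine pregnancy test, so a first dose could rest on a negative result up to about 13 weeks old if the parent final visit included that test

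*Combined protocol and SAP*

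**What the plan says.** Section 4.5 (Study Assessments) sets the rule for Day 1: "Assessments that were performed at the final visit of the parent study, if within 3 months prior to Day 1, should not be repeated". Footnote b of Appendix 1, attached to the Day 1 column, says the same: "Activities that were performed at final visit of the parent study, if within 3 months prior to Day 1, should not be repeated". Neither names an exception.

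The row "Pregnancy test (urine) women" in Appendix 1 is marked at Day 1 and then every 4 weeks. Footnote m adds, for the time on treatment: "The patient will be requested to conduct monthly urine pregnancy tests at the site between in-clinic study visits".

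Three other provisions bear on the point:

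- Section 4.1.2 (Exclusion Criteria): "Women of childbearing potential must have a negative urine pregnancy test result prior to initiation of the first dose of study drug". No maximum age of the test is given.
- Section 4.5.1: "All screening (Day 1) evaluations must be completed and reviewed to confirm that patients meet all eligibility criteria before enrollment". Again there is no limit on how old a result may be.
- Section 3.1: "Patients may enroll in this OLE study at any time after completing the treatment period of the parent study". The gap between the parent study and Day 1 is therefore not bounded.

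The contraception requirement in Section 4.1.1 applies "during the treatment period and for at least 4 weeks after the final dose of fenebrutinib". It does not reach back to the time before Day 1 of the extension.

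**The concern.** Carrying recent results forward is sensible for items that change slowly, such as a lipid panel. It does not work for a pregnancy test, because a negative result says nothing about conception after the sample was taken. The no-repeat rule treats both kinds of item alike, and its wording discourages a new test rather than merely allowing the old one to stand.

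What is at stake is avoidable exposure in early pregnancy. The plan clearly means to prevent it: pregnancy is an exclusion (Section 4.1.2) and a mandatory reason to stop drug (Sections 4.6.1 and 5.4.3.1), and testing on treatment is every 4 weeks. A woman who conceived between the parent final visit and Day 1 could nevertheless take 200 mg twice daily until the Week 4 test, when a Day 1 test could have found the pregnancy before any open-label dose.

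**Working it through.** **Does any text require a fresh test on Day 1?**

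- The no-repeat sentence in Section 4.5 and footnote b covers parent final-visit assessments in general, and the pregnancy test is one of the Day 1 items under footnote b.
- Section 4.1.2 asks for a negative result before the first dose. An 80-day-old negative result meets that wording.
- Section 4.5.1 asks that Day 1 evaluations be complete and reviewed. It does not say that a carried-forward result fails to count as complete.
- The qualifier about exceptions specified elsewhere, in the preceding sentence of Section 4.5, concerns whether Day 1 assessments come before dosing. It does not attach to the no-repeat sentence.
- Footnote m and Section 4.5.5 provide for tests at the specified visits and monthly between them. Neither sets aside footnote b on Day 1.

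No provision closes the gap.

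**Inputs**

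- Maximum age of a carried-forward assessment: 3 months (Section 4.5; Appendix 1 footnote b).
- Next scheduled test: Week 4, Day 28 ± 7 days (Appendix 1).
- Testing interval on treatment: 4 weeks, or 28 days (Appendix 1).

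**Age of the test at first dose.** The plan states 3 months; in days this depends on the calendar.

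- Shortest, February to April: 28 + 31 + 30 = 89 days; 89/7 = 12.7 weeks.
- Longest, for example July to September: 31 + 31 + 30 = 92 days; 92/7 = 13.1 weeks.
- In testing intervals: 89/28 = 3.2 and 92/28 = 3.3.

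**Day 1 to the Week 4 test**

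- Nominal: 28 − 1 = 27 days.
- Across the window: 21 − 1 = 20 days to 35 − 1 = 34 days.

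**Interval between consecutive tests**

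| Case | Nominal Week 4 visit | Across the ±7-day window |
|---|---|---|
| Parent test of maximum age carried forward | 89 + 27 = 116 to 92 + 27 = 119 days | 89 + 20 = 109 to 92 + 34 = 126 days (15.6 to 18.0 weeks) |
| Fresh test on Day 1 | 27 days | 20 to 34 days |

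The long interval is time without a test, not time on drug. Open-label exposure of a pregnancy already present at Day 1 runs from the first dose to the Week 4 test: 27 days nominally, 20 to 34 across the window.

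**The case against.** The strongest objection is that the problem depends on a document that is not available. The rule reaches the pregnancy test only if the parent study's final visit included one. If it did not, or if that visit was more than 3 months before Day 1, the test must be done on Day 1. This stands, and it limits how far the point can be taken. The extension schedules a urine pregnancy test at its own treatment discontinuation and completion/follow-up visits, which makes a similar parent schedule plausible but does not establish it. Whether contraception duties in the parent study cover part of the gap is also unknown; that bears on the chance of conception, not on the missing exception.

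A second objection is that the pregnancy-specific text should control. Section 4.1.2 is mandatory and sits under the pregnancy exclusion, and Section 4.5.5 and footnote m say tests are to be done at specified visits, whereas the no-repeat rule is general and advisory. A careful site could read it that way. But none of these provisions sets an age limit or overrides footnote b, so a site that relies on the parent result is also within the text. The intent is clear; the instruction does not deliver it.

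Third, other safeguards remain. Known pregnancy excludes the patient, and an investigator may test on suspicion. These narrow the risk to unrecognised pregnancies, which are the ones a routine test is meant to find.

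Finally, the 126-day figure requires both a test at the 3-month limit and the latest Week 4 visit. That is correct: it is an upper bound. Patients who roll over promptly are little affected.

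**Conclusion.** The concern holds. As written, the plan allows a woman of childbearing potential to start open-label fenebrutinib on a negative urine test up to 89 to 92 days old, with 109 to 126 days between consecutive tests in that limiting case, against 20 to 34 days if she were tested on Day 1. The avoidable open-label exposure of a pregnancy conceived in the gap lasts until the Week 4 test, nominally 27 days. A conception after a fresh Day 1 test would also go unseen until Week 4; that exposure is not due to this rule and is not counted.

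The conclusion assumes that the parent final visit included a urine pregnancy test and fell within 3 months before Day 1. The number of women affected cannot be estimated, because the parent schedule, the share of women of childbearing potential and the distribution of gaps are not given; it may be small or zero. No endpoint or analysis is affected. It should be fixed because the possible harm is one the protocol sets out to prevent and the remedy is nearly free. Confidence is medium: the gap in the wording is clear, but how often it would matter is not known.

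**What to change.** Add to Section 4.5 and to Appendix 1 footnote b, directly after the no-repeat sentence:

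> This does not apply to the urine pregnancy test, which must be performed on Day 1 before the first dose.

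In Section 4.1.2, state that the negative urine pregnancy test must be obtained on Day 1, before the first dose of study drug.

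The age of the test at first dose then falls from as much as 92 days to 0. The cost is one extra local urine test at an existing visit, and only for women of childbearing potential whose parent result would otherwise have been carried forward. Visits, endpoints and analyses do not change.

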4.5.1 Informed Consent Forms and Screening Log

Written informed consent for participation in the study must be obtained before performing any study-related procedures. Informed Consent Forms for enrolled patients and for patients who are not subsequently enrolled will be maintained at the study site.

All screening (Day 1) evaluations must be completed and reviewed to confirm that patients meet all eligibility criteria before enrollment and receiving the first open-label dose in this study. The investigator will maintain a screening log to record details of all patients screened and to confirm eligibility or record reasons for screening failure, as applicable.

4.5.2 Medical History, Concomitant Medication, and Demographic Data

Medical history, including clinically significant diseases, surgeries, cancer history (including prior cancer therapies and procedures), and reproductive status, will be recorded at baseline in the parent study. In addition, all medications (e.g., prescription drugs, over-the-counter drugs, vaccines, herbal or homeopathic remedies, nutritional supplements) used by the patient from the time the patient completed the treatment period of the parent study will be recorded. Past resolved adverse events will be recorded in the medical history if clinically significant. Refer to Section 5.3.5.3 for information on recording adverse events that had not resolved at the end of the parent study. At the time of each follow-up physical examination, an interval medical history should be obtained and any changes in medications and allergies should be recorded.

Demographic data will include age, sex, and self-reported race/ethnicity.

4.5.3 Physical Examinations

Limited, symptom-directed physical examinations should be performed at specified visits and as clinically indicated. Changes in parent study baseline abnormalities should be recorded in patient notes. New or worsened clinically significant abnormalities should be recorded as adverse events on the Adverse Event eCRF.

4.5.4 Vital Signs

Vital signs will include measurement of pulse rate and systolic and diastolic blood pressure while the patient is in a seated position for at least 5 minutes.

4.5.5 Laboratory, ██████████ and Other Biological Samples

Samples for the following laboratory tests will be sent to one or several central laboratories for analysis as per the schedule of activities:

- Hematology: hemoglobin, hematocrit, platelet count, RBC count, WBC count, and percent and absolute differential counts (neutrophils, bands, lymphocytes, monocytes, eosinophils, basophils, other cells)
- Serum chemistry: bicarbonate or total carbon dioxide (if considered standard of care for the region), sodium, potassium, chloride, glucose, BUN or urea, creatinine, calcium, phosphorus, magnesium, total and direct bilirubin, total protein, albumin, ALT, AST, lactate dehydrogenase, ALP, creatine phosphokinase, C-reactive protein, lipase, and uric acid
- Urinalysis, including dipstick (pH, specific gravity, glucose, protein, ketones, blood) and microscopic examination (sediment, RBCs, WBCs, casts, crystals, epithelial cells, bacteria)
- Coagulation: INR, aPTT, PT, and fibrinogen
- Lipid panel
- Plasma samples for PK analysis

The following laboratory tests will be sent to the site's local laboratory for analysis:

- Pregnancy test

For women of childbearing potential: Urine pregnancy tests will be performed at specified visits. The patient will be requested to conduct monthly urine pregnancy tests at the site between in-clinic study visits. If a urine pregnancy test is positive, it must be confirmed by a serum pregnancy test.

For sampling procedures, storage conditions, and shipment instructions, see the laboratory manual.

Unless the patient gives specific consent for his or her leftover samples to be stored for optional exploratory research, biological samples will be destroyed when the final Clinical Study Report has been completed, with the following exceptions:

- Plasma samples collected for PK analysis will be destroyed no later than 5 years after the final Clinical Study Report has been completed.

When a patient withdraws from the study, samples collected prior to the date of withdrawal may still be analyzed, unless the patient specifically requests that the samples be destroyed or local laws require destruction of the samples. However, if samples have been tested prior to withdrawal, results from those tests will remain as part of the overall research data.

Data arising from sample analysis will be subject to the confidentiality standards described in Section [8.4](#).

Given the complexity , data derived from these analyses will generally not be provided to study investigators or patients unless required by law. The aggregate results of any conducted research will be available in accordance with the effective Sponsor policy on study data publication.

